7.3.6 Unscheduled Visit

The investigator has the option of bringing a study subject back in for an unscheduled visit during the course of the study for safety reasons (e.g., subject complaint of moderate or severe ocular symptoms, and ADE). An unscheduled visit CRF should be completed. At minimum the investigator should record the following”

- a. Inspection of the punctal plug via the slit-lamp, if applicable
- b. Slit-Lamp examination
- c. Recording of any reported adverse device events

8 ASSESSMENT OF SAFETY

8.1 Safety Variables

Safety variable for this study include any clinically significant slit-lamp biomicroscopy findings, any extrusions of a punctal plug, and incidence and severity of any reported ADEs after punctal plug insertion. To optimize consistency of ADE reporting across centers, the study subject will be asked by study personnel the following question:

"Have you had any problems since your last visit?"

All ADEs either observed by the Investigator or one of his/her medical collaborators, or reported by the subject spontaneously, or in response to the direct question above, will be noted in the ADEs section of the subject's CRF and in the source document. Only treatment emergent ADEs (those occurring during or after the insertion of the investigational punctal plug) should be recorded as ADEs. Events reported before the initial screening period should be recorded as medical history.

If any ADE is reported, the date of onset, intensity, relationship to study device or treatment, action taken, date of resolution (or the fact that it is still continuing or has become chronic), and whether the ADE is serious or not will be recorded (see [Section 8.5](#)).

Plug migrations are to be reported as an ADE; however, a superficial migration, in which the plug is temporarily displaced, is visible with the slit lamp and can be easily removed, is not considered an ADE.

8.2 Definitions

8.2.1 Adverse Device Event (ADE)

Any unfavorable and unintended effect on health or safety of a study subject involving the use of a medical device. Medical conditions or diseases present before a subject starts the study are only considered adverse device events if they worsen during or after use of the medical device. Any new medical conditions or diseases that present during the course of the study will be recorded as an adverse device event.

8.2.2 Serious Adverse Device Event (SADE)

Defined as any ADE that:

- Results in death
- Is life-threatening even if temporary in nature.

NOTE: The term "life-threatening" refers to an event in which the subject was at risk of death at the time of the event; it does not refer to an event which hypothetically might have caused death if it were more intense

- Requires inpatient hospitalization or prolongs existing hospitalization
- Results in permanent impairment of a body function or permanent damage to a body structure
- Necessitates medical or surgical intervention to prevent a life-threatening situation or preclude permanent impairment of a body function or permanent damage to a body structure

8.2.3 Unexpected Adverse Device Event

An ADE that is not identified in nature, instructions for use or clinical study protocol.

8.3 Adverse Device Event Descriptions

8.3.1 Intensity

The intensity of ADEs will be characterized as mild, moderate, or severe, as follows:

Mild: Usually transient, requiring no special treatment, and does not interfere with the subject's daily activities

Moderate: Introduces a low level of inconvenience or concern to the subject and may interfere with daily activities, but is usually ameliorated by simple therapeutic measures

Severe: Significantly interferes with a subject's usual daily activities and requires systemic drug therapy or other treatment, if available

8.3.2 Relationship to Study Device

The causal relationship to study device will be determined by the investigator according to his/her best medical judgment, as follows:

Suspected: There is a reasonable possibility that the ADE is associated with use of the study device, such as a temporal relationship of the event to study device insertion, or when other drugs, therapeutic interventions, or underlying conditions do not provide a sufficient explanation for the observed event.

Not suspected: A relationship between the ADE and the study device can reasonably be ruled out based on lack of any temporal relationship of the event to study device insertion, or when the subject's underlying condition, medical history, or other therapy provide sufficient explanation for the observed event.

8.4 Follow-up for Adverse Device Event

Throughout the study to the final study contact, all ADEs will be followed until they resolve or become chronic (as judged by the investigator).

At the final study visit, new ADEs, as well as follow-up information for continuing ADEs, will be recorded in the CRF and source document. If an SADE (defined in [Section 8.2.2](#)) is unresolved at the final study visit, it will be followed by the investigator until it resolves or becomes chronic (as judged by the investigator). Follow-up data for such SADEs will be recorded in the source document and reported to the safety monitors (refer to [Section 8.5.2](#)). Non-serious ongoing ADEs will be followed beyond the final study visit at the discretion of the Investigator and recorded in the source documents.

8.5 Reporting Procedures

Adverse device events that occur from Visit 1 through completion of the end-of-study visit must be documented. The Investigator will assess the ADE severity and relationship of the ADE to the study device. The Investigator will follow the progress of the study subject until the ADE either resolves or becomes medically stable. Treatments and medications required to treat ADEs must be recorded.

All adverse device events, regardless of severity and whether or not attributed to the device are to be reported to Mati Therapeutics Inc. Adverse device events are also to be reported to the site IRB per the IRB's reporting requirements.

8.5.1 Adverse Device Event Reporting

An adverse device event that is not serious or related to the study device is to be reported to the designated Medical Monitor within 10 working days of the Investigator first becoming aware of the event. Notification will occur by recording on the appropriate CRF(s), scanning and email or faxing the CRF(s) of the visit in which the event is first noted. An adverse device event is also to be reported to the reviewing IRB/IEC per his/her reporting requirements.

8.5.2 Serious Adverse Device Event Reporting

All SADEs, regardless of cause(s) or relationship to the study device, must be reported within 24 hours of becoming aware of the event to the designated Medical Monitor by telephone, facsimile, or email. Additional contact numbers and ADE/SADE reporting information will be provided to each site in a separate document.

All SADEs will be reported to:

[name] or	[name]
Mati Therapeutics Inc.	Mati Therapeutics Canada Inc. (R&D Branch)
[contact]	[contact]
[contact]	[contact]
[contact] (cell)	
[contact]	

The Investigator must complete the SADE Report Form and send it with other relevant pages of the CRF to the designated Medical Monitor within 24 hours of discovery of the SADE. The Investigator will also compile with urgent priority other relevant documentation (copies of test results, hospital discharge summary, autopsy report, etc.) and send this information to the designated Medical Monitor. Any SADE will be reported to the Investigator's IRB/IEC per his/her reporting requirements.

8.5.3 Unanticipated Problem Reporting

If during the study an adverse device event occurs that may reasonably be regarded as study-device-related and was not previously expected in nature, severity, or degree of incidence in the investigation plan, the Investigator is to report the unanticipated adverse device event to the designated Medical Monitor within 48 hours, and to the Investigator's IRB as soon as possible, but no later than 10 working days, after learning of the event as required by 21CFR812.

8.6 Reporting of Technical Complaints about Investigational Device

8.6.1 Definitions

A quality complaint received in writing, electronically, or orally that alleges deficiencies related to the identity, quality, durability, reliability, safety, effectiveness, or performance of a device product. (In this definition, "effectiveness" refers to the actual function of the device, not to how

the subject responds to the action of the device. Also in this definition, "device product" refers only to devices provided by the Sponsor for clinical studies and to investigational devices.)

In this definition, safety includes the safety of a subject, user, or other person associated with the use of a medical device.

8.6.2 Reporting of Technical Complaints

Any technical complaint should be reported by fax to the Sponsor's Chief Scientific Officer (contact information below) within 24 hours. The complaint report should include the following information:

- Name of the study device
- Model of the study device
- Identification numbers (i.e. serial or part number) for a device
- Investigator name, study center name, and contact number
- Date the complaint occurred
- Brief description of the complaint
- Study subject or other individual involved (yes/no):
 - If yes and a study subject, the investigator should report whether any ADEs were associated with the complaint (yes/no; if a subject ADE was associated with the complaint, refer to [Section 8](#) and attach the ADE CRF page to the complaint)
 - If yes and another individual, the investigator should describe the situation and any ill effects on the health of the individual
 - If no, in the investigator's judgment, the investigator should report whether the complaint could reasonably cause an SADE if it recurred under circumstances that did involve a study subject or other person (yes/no).
- Identity of any other investigational or commercial devices involved.

The study device and associated packaging that initiated the complaint should be returned to the Chief Scientific Officer (address below) for analysis.

Mati Therapeutics Inc.
Attn: Chief Scientific Officer, [name]
[name]
[name]
[name]
[contact]
[contact]

Any complaint about a study device must be reported regardless of whether the defect or deficiency had any effect on a subject or on study personnel.

8.6.3 Punctal Plug SADE and Technical Complaints

The Sponsor will evaluate all SADE reports and technical complaints received in the study to determine if the report meets the definition of an unanticipated ADE. Unanticipated ADEs are defined as follows:

- any serious adverse effect on the health or safety or any life-threatening problem or death caused by, or associated with, a device, if that effect, problem, or death was not previously identified in nature, severity, or degree of incidence in the investigational plan or application or any other unanticipated serious problem associated with a device that relates to the rights, safety, or welfare of subjects.

If the Sponsor determines that any SADE or technical report is an unanticipated ADE, an investigation will be begun immediately. The Sponsor will inform the investigator of any additional reporting requirements beyond those stated in [Section 8.5.3](#) as applicable.

If the Sponsor determines that an unanticipated ADE presents an unreasonable risk to subjects, the Sponsor will terminate the study as soon as possible. Termination will occur not later than five working days after the Sponsor makes this determination and not later than 15 working days after the Sponsor first received notice of the effect. The Sponsor will report the results of any investigations to the FDA and to investigators, who will also submit the reports to his/her IRBs, within 10 working days after the Sponsor first received notice of the effect.

8.6.4 Anticipated Adverse Device Events

Due to the duration of the study, the only anticipated ADE would be extrusion of the punctal plug. Any event that is unlikely but anticipated must have an adverse device event form completed and reported to Mati Therapeutics Inc. (see [Section 8.5](#) for reporting details).

8.7 Study Halting Rules

Collaboration between representatives of Mati Therapeutics Inc., Investigators and statisticians may stop the study if there is evidence of a lack of safety associated with the study device.

8.8 Safety Oversight

This study will utilize a Medical Monitor for safety monitoring. The Medical Monitor will review and assess any reports of adverse device events and, if necessary, to discuss these with the reporting Investigator(s). The medical monitor will also be available to answer all questions from Investigators.

9 CLINICAL MONITORING

Mati Therapeutics Inc. representative will ensure that the investigation is conducted in accordance with the following:

- a. GCPs as specified in ICH E6 (R1) and E8 (8.2) and 21 CFR. Parts 50, 54, 56 and 812
- b. The signed Investigators' Agreement
- c. The signed protocol for the study
- d. Any conditions imposed by the IRB
- e. The requirements of the regulations for the Protection of Human Patients (21CFR50) and all other applicable regulations

Prior to initiation of the study at a site, the CRA will conduct a visit with the Investigator(s) and the study staff to ensure the following:

- a. The Investigator understand the investigational status of the study material and the requirements for its accountability
- b. The Investigator understands the protocol and understands and accepts his/her obligations in conducting the clinical investigation
- c. The Investigator has adequate facilities for conducting the study, and equipment and instrumentation required by the protocol
- d. The Investigators and his/her staff have sufficient time and access to an adequate number of subjects to conduct the clinical investigation.

During the course of the investigation, the CRA may conduct periodic site visits and maintain telephone contact with the Investigators and his/her staff to ensure that the study is being conducted in accordance with the protocol, and with any specific conditions of the IRB and clinical requirements. At such visits, the CRA will ensure that informed consent has been obtained and documented for each study subject, in accordance with 21 CFR parts 50 and 56, and the requirements of the overseeing IRB and the Sponsor. The CRA will review and compare CRFs to source records and supporting documents to ensure that data recorded on the CRFs are complete, accurate, and legible, and that any corrections to the CRFs are made with a single line strike-through of the incorrect entry, and entry of the correct information adjacent with initials of the individual making the correction and date of corrected entry. The CRA will further ensure that there are no data omissions and that any study subject withdrawals are documented. The CRA will review CRFs and source records for any unanticipated ADEs, and ensure that the Investigators are complying with FDA and Sponsor requirements for reporting ADEs and SADEs. The CRA will ensure that the Investigators are carrying out the agreed upon activities and have not delegated them to unauthorized staff, that the facilities and staff continue to be acceptable for the study, and that the Investigators are properly tracking study inventory and are accounting for the disposition of all study devices.

The CRA shall prepare and maintain records of each site visit, significant telephone discussion, and written communications with the site. These records will include such information as:

- a. Date, name, and address of the Investigators and names of other staff members present at each meeting
- b. A summary of the findings of the visit
- c. A statement of any action taken by the CRA or Investigators to correct any deficiencies noted.

10 STATISTICAL CONSIDERATIONS

10.1 Statistical and Analytical Plans

The primary analysis population will be an ITT (Intent-to-Treat) analysis for all study subjects who had a lower puncta inserted with a study punctal plug and had no major protocol violations. Individual study subjects or individual visits may be excluded if a major protocol violation occurs (such as violation of inclusion/exclusion criteria or non-compliance with protocol requirements that can potentially have significant impact on study outcomes).

10.2 Statistical Hypotheses

10.2.1 Primary Hypotheses

The Null Hypothesis: There are no differences between baseline and follow-up tear lake evaluations

Alternative Hypothesis: There are differences between baseline and follow-up tear lake evaluations

10.2.2 Secondary Hypotheses

The Null Hypothesis: There are no differences in the frequency or severity of study subjects exhibiting of epiphora

Alternative Hypothesis: There are differences in the frequency or severity of study subjects exhibiting of epiphora

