- a. A male or female subject, 18 years of age or older, in good general health at the time of the baseline examination, who may or may not have a mild to moderate dry eye condition
- b. A subject must be able to read, comprehend and be willing to give HIPAA authorization and informed consent

- c. A subject must be willing to have a punctal plug inserted in the lower punctum of one of their eyes
- d. A subject must be willing to comply with all study instructions, agree to make all office appointments, and complete the entire course of the study

Subject Exclusion Criteria: The following are exclusion criteria for potential study subjects' wishing to participate in this study:

- a. A subject with a history of complications, adverse events, trauma or disease in the nasolacrimal area, whether or not it was due to punctal plug wear, including but not limited to dacryocystitis, inflammation or canaliculitis in the planned study eye
- b. A subject with a history of intolerance to punctal plugs
- c. A subject with structural lid abnormalities (e.g., ectropion, entropion) in the planned study eye
- d. A subject with any clinically significant lid, conjunctival or corneal findings in the planned study eye at the baseline visit
- e. A subject with a puncta >0.9 mm prior to dilation in the planned study eye
- f. A subject with a severe dry eye condition
- g. A subject experiencing epiphora in the planned study eye
- h. A subject experiencing any clinically significant ocular pain or discomfort in or around either eye at the baseline visit
- i. A subject with a known sensitivity to any inactive ingredient of the punctal plug, silicone, topical anesthetic, or any other products required for the study
- j. A subject currently participating or has participated in a clinical trial involving the use of an investigational medication within 30 days prior to enrollment.

Study Duration: The approximate study duration is eight months. The study is projected to start the 3rd quarter of 2019

Study Variables: The following will be performed and/or recorded during the course of the study

Visit 1: Screening/Baseline (Day 0)

- a. Obtain written Consent and HIPAA
- b. Subject demographic data and medical history for past 7 days
- c. Verify a subject has not used any ocular drops within the last hour prior to their baseline visit

- d. Record subject reports of any ocular signs or symptoms they are currently experiencing, prior to the sizing and dilation of the lower punctum

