4.2 Study Endpoints

The study will be complete when up to 40 study subjects (40 eyes) have been evaluated at Visit 3 (28 + 4 days post-insertion) or have been terminated from the study.

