5.3 Study Subject Exclusion Criteria

The following are exclusion criteria for potential study subjects' wishing to participate in this study:

- a. A subject with a history of complications, adverse events, trauma or disease in the nasolacrimal area, whether or not it was due to punctal plug wear, including but not limited to dacryocystitis, inflammation or canaliculitis in either eye
- b. A subject with a history of intolerance to punctal plugs
- c. A subject with structural lid abnormalities (e.g., ectropion, entropion) in either eye
- d. A subject with any clinically significant lid, conjunctival or corneal findings in either eye at the baseline visit
- e. A subject with a puncta >0.9 mm prior to dilation in either eye
- f. A subject with a severe dry eye condition
- g. A subject experiencing epiphora in either eye
- h. A subject experiencing any clinically significant ocular pain or discomfort in or around either eye at the baseline visit
- i. A subject with a known sensitivity to any inactive ingredient of the punctal plug, silicone, topical anesthetic, or any other products required for the study
- j. A subject currently participating or has participated in another clinical trial within 30 days prior to enrollment.

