5.5.1.3 Disqualification from the study

A study subject will be disqualified from the study if there was a failure to obtain written informed consent or HIPAA Authorization, improper entry (did not meet all inclusion/exclusion criteria).

Notification of disqualification will be clearly documented on the appropriate Case Report Form. The Investigator must make every effort to have the study subject return to the clinic for an end of study safety evaluation and the removal of the punctal plug. A study subject disqualified from the study will be replaced.

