7.3 Study Visit Schedule

7.3.1 Visit 1: Day 0 - Screening (Prior to punctal plug insertion)

A potential study subject qualifications will be assessed according to the inclusion/exclusion criteria listed in the protocol (see Sections 5.2 and 5.3). Prior to undergoing any study-specific procedures, both the study Informed Consent and Authorization for Use/Disclosure of Health Information forms (HIPAA authorization) must be signed by a potential subject who has agreed to participate in the study. During this visit, the following information will be collected/evaluated and recorded in the appropriate sections of the study case report forms of a subject, prior to the sizing and dilation of the lower punctum for the planned study eye.

- a. Obtain informed consent and HIPAA authorization release
- b. Record the subject's demographic data and prior 7 days medical history
- c. Verify a subject has not used any ocular drops within the last hour prior to their baseline visit
- d. Record any subject reports of ocular signs or symptoms they are currently experiencing
- e. Slit-lamp examination of the planned study eye

7.3.2 Visit 1:Baseline - Day 0 (Insertion of a punctal plug - refer to Section 6.2 for details regarding the insertion of the NDE punctal plug)

After the screening examination, a qualified study subject will be sequentially assigned an ID number. In addition, the ID number and the study subject initials will be recorded on study case report forms, in lieu of recording his/her name, in order to maintain subject confidentiality.

Note: The investigator has the option of inserting the plug in either the left or right eye of the subject. However, if the investigator is unable to insert the plug in the first eye chosen, the investigator can insert the plug in the fellow eye as long as the fellow eye meets all study inclusion/exclusion criteria.

- f. Tear lake evaluation of the planned study eye prior to the sizing and dilation of the lower punctum
- g. Size evaluation of the punctum of the planned study eye prior to the dilation of the lower punctum
- h. After dilation, the study punctal plug is inserted in to the lower punctum of study eye, inspect the punctal plug using the slit-lamp, the position of a study punctal plug may be adjusted with forceps.
- i. Record any reported adverse device event(s)

j. After the study plug has been inserted in the lower puncta, the investigator will assess the insertion characteristics of the plug.

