10.4 Description of Statistical Methods

10.4.1 General Approach

All statistical tests will be two-sided and interpreted at a 5% significance level. Descriptive statistics (i.e., mean, standard deviation, etc.) will be provided for all continuous variables and frequency distributions will be generated for all categorical variables collected in this study.

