10.4.3 Analysis of the Secondary Endpoint(s)

Secondary endpoints will be based on changes from baseline in the severity of epiphora. For the investigator's evaluation of the subject's acceptance of the punctal plug, data from all subjects will be evaluated. Investigator evaluation of insertion and removal characteristics will be tabulated by study subject and overall evaluation. For analyses using the intent-to-treat (ITT) data set, all data from all subjects with at least one assessment of epiphora, subject acceptability and punctal plug characteristics evaluations will be included. For the per protocol (PP) analyses dataset, data from subjects or visits with significant protocol deviations will be excluded.

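### Eligibility fixes baseline epiphora at none, so the secondary no-differences hypothesis should become an estimate of new epiphora with an exact confidence interval

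*Combined protocol and SAP*

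**What the plan says.** **Hypothesis and analysis.** Section 10.2.2 gives the secondary null as "There are no differences in the frequency or severity of study subjects exhibiting of epiphora", without naming a comparator or time points. Section 10.4.3 supplies the comparison: "Secondary endpoints will be based on changes from baseline in the severity of epiphora". Section 10.4.1 adds: "All statistical tests will be two-sided and interpreted at a 5% significance level". No test for epiphora is named anywhere.

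**Entry criteria.** Section 5.3, exclusion (g), removes "A subject experiencing epiphora in either eye". The Synopsis version removes "A subject experiencing epiphora in the planned study eye". Neither sets a severity threshold. If the first eye cannot be plugged, the Synopsis and Section 7.3.2 say that "the investigator can insert the plug in the fellow eye as long as the fellow eye meets all study inclusion/exclusion criteria". Section 5.5.1.3 disqualifies and replaces a subject for "improper entry (did not meet all inclusion/exclusion criteria", and Section 10.1 defines the primary population as plugged subjects without major violations, giving eligibility violations as an example.

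**Size.** Section 4.2: "The study will be complete when up to 40 study subjects (40 eyes) have been evaluated at Visit 3" or have been terminated. Section 10.5 states that no formal sample size estimation was done, because this is a pilot.

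**Epiphora elsewhere.** Section 2.3 lists it among the risks of punctal plugs. Section 4.2.2 names it among the secondary endpoints, and it is the only one of them with a stated hypothesis.

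**The concern.** The entry criteria and the hypothesis do not fit together. If no eligible plugged eye has epiphora at baseline, baseline is a constant and not a measurement to compare against. No eye can improve, and every case at follow-up is new. A comparison with baseline is then an indirect way of asking how many plugged eyes develop epiphora and how severe it is.

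This affects how the result is read. In a small study, a handful of new cases can give a non-significant p-value, and the stated null would then stand although every one of those cases arose after insertion. Epiphora is a listed plug risk, so a reader needs the rate and its uncertainty. A p-value against a baseline of zero gives neither. The mismatch would remain even if epiphora were recorded perfectly at every visit.

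**Working it through.** The plan gives no power, expected epiphora rate or detection threshold, so it has no figure of its own to reproduce.

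**Step 1: baseline in the plugged eye.**
- Section 5.3 (g) bars epiphora in either eye, so the plugged eye has none.
- Synopsis (g) bars it in the planned study eye, so again the plugged eye has none. The two versions need reconciling, but the difference does not change this result.
- A switched fellow eye must meet the same criteria, so it has none.
- Ineligible entries are disqualified and replaced (5.5.1.3), and they fall outside the population in 10.1.

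No eligible plugged eye can therefore show a reduction.

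**Step 2: the paired test.** Let k be the number of eyes with new epiphora. The discordant pairs are k worsened and 0 improved. The exact McNemar (sign) test gives two-sided p = 2 × 0.5^k:
- k = 4: 2 × 0.0625 = 0.125
- k = 5: 2 × 0.03125 = 0.0625
- k = 6: 2 × 0.015625 = 0.031

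The result is the same if severity is graded. Every non-zero change is still a worsening, so a sign test on severity, or an exact signed-rank test, also gives 2 × 0.5^k.

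**Step 3: dependence on the test.** The exact test is an assumption. Other standard choices, two-sided with 40 eyes:

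| Test | Most new cases without significance | p there | p with one more case |
|---|---|---|---|
| Exact McNemar or sign | 5 | 0.0625 | 0.031 |
| McNemar, continuity-corrected, (k − 1)²/k on 1 df | 5 | 0.074 | 0.041 |
| Fisher, unpaired, k/40 against 0/40 | 5 | 0.055 | 0.026 |
| McNemar mid-p, 0.5^k | 4 | 0.0625 | 0.031 |
| McNemar, uncorrected, k on 1 df | 3 | 0.083 | 0.046 |
| One-sample t on 0/1 change | 3 | 0.083 | 0.044 |

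The range is 3 to 5. A one-sided exact test at 5% gives 0.0625 for 4 cases and 0.031 for 5, so it would still leave 4 cases non-significant.

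**Step 4: what the same counts show as an incidence.** Exact (Clopper-Pearson) 95% intervals with 40 eyes:
- 0/40: 0% (0 to 8.8%); upper limit 1 − 0.025^(1/40) = 0.088
- 3/40: 7.5% (1.6% to 20.4%)
- 5/40: 12.5% (4.2% to 26.8%)
- 6/40: 15.0% (5.7% to 29.8%)

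Forty is a ceiling. The exact-test threshold does not depend on the number of eyes, so 5 cases would be 16.7% of 30 eyes (5.6% to 34.7%) or 25% of 20 (8.7% to 49.1%).

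**Step 5: chance of reaching significance.** With 40 eyes and the exact test (6 or more cases needed), the probability is 0.21, 0.57 and 0.84 at assumed true incidences of 10%, 15% and 20%. The documents give no rate, so these are illustrations.

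**The case against.** The strongest reply is that new cases would be seen anyway. Section 10.4.1 promises frequency distributions for all categorical variables. With no epiphora at baseline, a table by visit is already the count of new cases. Section 10.4.4 summarises adverse device events by preferred term and severity without any test, and subjects are asked at each visit about problems since the last one. Symptomatic epiphora could well be captured that way. This stands in part: the counts would not be wholly hidden. But neither section promises a confidence interval, Section 8.6.4 names only extrusion as an anticipated event, and neither route changes the null in 10.2.2.

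A second reply is that this is a pilot with no sample size calculation, so low power is expected. That is true, and it favours estimation over a test whose non-significance says little.

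Three stronger readings are tempting, and the documents do not support them:
- A reader might take 5 of 40 as the plan's own threshold. No test is named, so the figure is 3 to 5 depending on the choice, and 40 is only a maximum.
- A reader might blame the two-sided test. It is a minor factor: the one-sided exact test still leaves 4 cases non-significant.
- A reader might call the comparison invalid, or infer that the sponsor will report no difference without counts. The exact test controls type I error, and nothing in the plan says that the counts will be withheld.

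Nor do the documents make epiphora the main tolerability question. Section 3 does not mention it; it is one of several secondary endpoints.

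**Conclusion.** The point holds as a mismatch between the entry criteria and the secondary hypothesis. Every eligible plugged eye is free of epiphora at baseline, so the analysis in 10.4.3 can show only no change or worsening, and 10.2.2 is in substance a question about incidence. As worded, the null could stand with up to 5 new cases under an exact McNemar or sign test, and with 3 to 5 across standard tests. With 40 eyes, that is 7.5% to 12.5% of eyes, with upper confidence limits of 20.4% for 3 cases and 26.8% for 5.

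The conclusion about baseline rests on eligibility being respected. The numbers rest on an assumed test and on 40 evaluable eyes; with fewer eyes, the same counts are a larger share. The harm lies in interpretation and presentation, and the planned frequency tables and event summaries soften it. The change should still be made, because it is cheap and answers the question the data can address.

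**What to change.** - Replace the hypothesis in 10.2.2 and the change-from-baseline wording in 10.4.3 with an estimate: the proportion of plugged eyes with new epiphora at Day 7, at Day 28 and at any time after insertion, each with its denominator and an exact (Clopper-Pearson) 95% confidence interval, plus a table by severity.
- State that epiphora is absent at baseline in the plugged eye by eligibility, and reconcile the two versions of exclusion (g).
- Drop the test. If one is kept, name it and state that a non-significant result will not be read as no difference.
- Add one graded epiphora item to the CRF at the existing visits, with the grades defined. The procedures in 7.2.1, the visit lists in 7.3 and the schedule contain no epiphora assessment or severity scale, so rewording alone would not deliver the estimate.

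The cost is wording in two sections, the reconciliation of exclusion (g) and one CRF item, with no extra visits or subjects. The sponsor gives up a no-difference claim on epiphora.
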